3.2 Phase II Dose Expansion

Following the identification of the MTD and/or RP2D in Phase I, patients may be enrolled into the 3 Phase II expansion cohorts (NSCLC, urothelial carcinoma, and synovial sarcoma) to make a preliminary assessment of the anti-tumor activity of IMCnyeso as a single agent in these disease settings. Initially, up to 9 patients may be enrolled in each Phase II cohort. If there is at least one response, at the discretion of the Sponsor up to an additional 15 patients may be accrued for a total of up to 24 patients, as discussed in [Section 9.9.2](#).

3.3 Patient Population

In Phase I, HLA-A*02:01-positive patients with a diagnosis of NY-ESO-1 and/or LAGE-1A positive advanced NSCLC, melanoma, urothelial carcinoma, or synovial sarcoma will be enrolled. In Phase II, HLA-A*02:01 positive patients with NY-ESO-1 and/or LAGE-1A positive advanced NSCLC, urothelial carcinoma, or synovial sarcoma will be enrolled and treated at the RP2D. All patients meet all eligibility criteria (see [Section 5](#)).

3.4 Definition of Study Periods

The study is made up of 6 study periods: (1) Pre-screening, (2) Screening, (3) Treatment, (4) Safety Follow-Up, (5) Disease Progression Follow-Up, and (6) Survival Follow-Up. The individual study periods are described in [Section 7](#).

3.5 End of Treatment

IMCnyeso will be administered according to the protocol-defined regimen until the patient meets criteria for treatment discontinuation described in [Section 6.16](#).

3.6 Definition of End of Study

An individual patient may end participation in the study for reasons listed in [Section 6.19](#).

The planned end of the study occurs when:

- A minimum of 80% of patients have completed the follow-up for disease progression or have discontinued the study for any reason,
- All patients have completed treatment and the Safety Follow-Up Period, and
- The endpoints of best overall response (BOR), OS, progression-free survival (PFS), and duration of response (DoR) have been adequately assessed in all subjects.

Please refer to [Section 9](#) for details of timing of the primary analysis and final reporting of data.

3.7 Early Study Termination

The study can be terminated at any time, for any reason by the Sponsor. Should this be necessary, any ongoing patient should be seen as soon as possible for an End of Treatment (EOT) visit (see [Section 7.3](#)).

The Investigator may be informed of additional procedures to be followed to ensure that adequate consideration is given to the protection of the patient's interests. Under guidance of the Sponsor, the Investigator will be responsible for informing the Institutional Review Board (IRB) and Independent Ethics Committee (IEC) of the termination of the study.

3.8 Post-Study Access to Treatment

As IMCnyeso is an investigational medication and not currently licensed for sale in any region, the drug is not available to patients outside of the study protocol.

4 STUDY OBJECTIVES AND ENDPOINTS

Study objectives and corresponding endpoints are shown in [Table 4-1](#).

Table 4-1: Study Objectives and Endpoints

Objectives	Endpoints
Primary - Phase I	
To identify the MTD and/or the RP2D of IMCnyeso, as a monotherapy, when administered weekly to patients with advanced NSCLC, melanoma, urothelial cancer, and synovial sarcoma	Incidence of dose-limiting toxicities Incidence and severity of AE and SAE Changes in laboratory parameters, vital signs, and ECGs Dose interruptions, reductions, and discontinuations
Primary – Phase II	
To assess the preliminary anti-tumor activity of IMCnyeso as monotherapy in advanced NSCLC, urothelial cancer, and synovial sarcoma	BOR as determined by RECIST v1.1
Secondary- Phase II	
To characterize the safety and tolerability of IMCnyeso	Incidence and severity of AE and SAE Changes in laboratory parameters, vital signs, and ECGs Dose interruptions, reductions, and discontinuations
Secondary- Phase I and Phase II	
To assess the preliminary anti-tumor activity of IMCnyeso as monotherapy	Phase I: BOR, PFS, and DoR by RECIST v1.1; OS Phase II: PFS, and DoR by RECIST v1.1; OS
To characterize the PK profile of IMCnyeso as monotherapy	Serum PK parameters (eg, AUC, C _{max} , T _{max} , t _{1/2}) after single and multiple doses
To evaluate the preliminary incidence of anti-IMCnyeso antibody formation following multiple infusions of IMCnyeso	Incidence of anti- IMCnyeso antibody formation and its impact on PK
Exploratory	
[REDACTED]	[REDACTED]

Objectives	Endpoints
[REDACTED]	[REDACTED] [REDACTED] [REDACTED]
[REDACTED]	[REDACTED] [REDACTED] [REDACTED]

AE = adverse event; AUC = area under the curve; BOR = best overall response; CD# = cluster of differentiation #; C_{max} = maximum observed concentration; [REDACTED]; [REDACTED]; DoR = duration of response; ECG = electrocardiogram; [REDACTED]; [REDACTED]; MTD = maximum tolerated dose; NSCLC = non-small cell lung cancer; [REDACTED]; PFS = progression-free survival; PK = pharmacokinetic; RECIST = Response Evaluation Criteria in Solid Tumors; [REDACTED]; RP2D = recommended Phase II dose; SAE = serious adverse event; t_{1/2} = terminal elimination half-life; [REDACTED]; T_{max} = time of maximum concentration; [REDACTED].

5 POPULATION SELECTION CRITERIA

5.1 Patient Population

To fulfill the study objectives, it is essential that appropriate patients are enrolled. The following eligibility criteria are designed to select patients for whom protocol treatment is considered appropriate. Patient eligibility should be reviewed and documented by an appropriate member of the site study team.

5.2 Inclusion Criteria

Patients must meet all the following inclusion criteria to be eligible for inclusion in the study:

General

1. Male or female patients age \geq 18 years of age at the time of informed consent
2. Ability to understand and provide written informed consent prior to undergoing any study procedures
3. Life expectancy of > 3 months as estimated by the Investigator
4. Eastern Cooperative Oncology Group (ECOG) Performance Status of 0 or 1 at Screening
5. In the opinion of the Investigator, all other relevant medical conditions must be well-managed and stable for at least 28 days prior to first administration of study drug

HLA and Tumor Antigen Testing

6. HLA-A*02:01 positive as confirmed by the central laboratory
7. NY-ESO-1 and/or LAGE-1A positive tumor confirmed by the central laboratory

Phase I: Disease Under Study and Prior Anti-Cancer Treatment

8. Histologically confirmed diagnosis of advanced NSCLC, melanoma, urothelial carcinoma, or synovial sarcoma
9. Patients must be relapsed from, refractory to, or intolerant to all approved and available classes of therapy known to provide clinical benefit for their condition

Phase II: Disease Under Study and Prior Anti-Cancer Treatment

10. Histologically confirmed diagnosis of advanced NSCLC, urothelial carcinoma, or synovial sarcoma
11. Measurable disease per Response Evaluation Criteria in Solid Tumors (RECIST) v.1.1 criteria ([Section 13.1](#))
12. A minimum of 10 patients enrolled in Phase II must have disease that is amenable to biopsy, and consent to provide biopsies during Screening and on treatment
13. Patients will have received the following previous therapies. These therapies must have been given for unresectable / metastatic disease or given in the adjuvant setting if disease progression occurred during or within 6 months of completing adjuvant therapy
 - NSCLC — PD-1/PD-L1 inhibitor. Patients with a genomic tumor aberration (eg, EGFR, ALK) that is targeted by Health Authority-approved agent(s) must be relapsed from, refractory to, or intolerant of relevant targeted agent(s)
 - Urothelial cancer — PD-1/PD-L1 inhibitor
 - Synovial sarcoma — at least 1 prior systemic chemotherapy regimen

Contraception

14. Female patients should either be of non-childbearing potential or must agree to use highly effective methods of contraception from Screening until 6 months following administration of the last dose of study drug (see [Section 6.14](#))
15. Male patients must be surgically sterile or use double barrier contraception from enrollment through treatment and for 6 months following administration of the last dose of study drug

5.3 Exclusion Criteria

Patients with any of the following will not be included in the study:

Disease Under Study and Prior Anti-Cancer Treatment

1. Presence of symptomatic or untreated central nervous system (CNS) metastases, leptomeningeal disease, cord compression, or CNS metastases that require doses of corticosteroids within 3 weeks prior to the planned first administration of study drug.
NOTE: Asymptomatic and adequately treated CNS metastases are not exclusionary provided the patient is neurologically stable

2. Systemic anti-cancer therapy for the disease under study within 2 weeks of the planned first administration of study treatment. For cytotoxic or immunotherapy agents that can present with major delayed toxicity (eg, anti-CTLA-4), a 4-week washout period is required
3. Radiotherapy within 2 weeks of the planned first administration of study drug. **NOTE:** palliative radiotherapy to a limited field, such as for the treatment of bone pain or a focally painful tumor mass, is not exclusionary
4. Presence of National Cancer Institute Common Terminology Criteria for Adverse Events (NCI CTCAE) \geq Grade 2 toxicity due to prior cancer therapy (except Grade 2 alopecia, stable Grade 2 peripheral neuropathy, Grade 2 endocrine disorder [on stable replacement doses and without symptoms], Grade 2 hypophosphatemia [on appropriate replacement therapy] and Grade 2 ototoxicity)

Laboratory Parameters

5. Patient with any out-of-range laboratory values defined as shown below. Hematology evaluations must be performed \geq 7 days after any blood or blood product transfusion and \geq 14 days after any dose of hematologic growth factor.
 - Creatinine clearance (calculated using Cockcroft-Gault formula or measured) < 40 mL/min
 - Total bilirubin $> 1.5 \times$ upper limit of normal (ULN); **NOTE:** for patients with Gilbert's syndrome; exclude if total bilirubin $> 3.0 \times$ ULN or direct bilirubin $> 1.5 \times$ ULN
 - Alanine aminotransferase (ALT) $> 3 \times$ ULN
 - Aspartate aminotransferase (AST) $> 3 \times$ ULN
 - Absolute neutrophil count (ANC) $< 1.0 \times 10^9/L$
 - Absolute lymphocyte count $< 0.5 \times 10^9/L$
 - Platelet count $< 75 \times 10^9/L$
 - Hemoglobin < 8 g/dL

Medical History and Concomitant Medications

6. Any active manifestations of autoimmune disease of the skin, including psoriasis and scleroderma, or history of severe skin manifestation of graft versus host disease

7. Clinically significant cardiac disease or impaired cardiac function including any of the following:
 - Clinically significant and/or uncontrolled heart disease such as diagnosed congestive heart failure (New York Heart Association Class ≥ 2), uncontrolled hypertension, or clinically significant arrhythmia currently requiring medical treatment
 - Confirmed manually over-read QT interval corrected by Fredericia's method (QTcF) > 470 msec on Screening ECG or known history of congenital long QT syndrome
 - History of acute myocardial infarction or unstable angina pectoris < 6 months prior to planned first administration of study drug
8. Active infection requiring systemic antibiotic therapy. **NOTE:** Patients requiring systemic antibiotics for infection must have completed treatment with any IV antibiotics at least 14 days before the planned first administration of study drug and any oral antibiotics at least 7 days before the planned first administration of study drug
9. Known history of human immunodeficiency virus (HIV) infection. Testing for HIV status is not necessary unless clinically indicated
10. Active hepatitis B virus (HBV) or hepatitis C virus (HCV) infection as defined per institutional protocol. Testing for HBV or HCV status is not necessary unless clinically indicated or the patient has a history of HBV or HCV infection
11. Patients receiving systemic treatment with steroid therapy (ie, prednisone > 10 mg daily [QD] or the equivalent) or any other immunosuppressive medication at any dose level that could interfere with the action of the study drugs, in the opinion of the Principal Investigator
 - Treatment for well controlled and asymptomatic adrenal insufficiency is permitted provided the patient has no history of adrenal crisis and replacement dosing is limited to prednisone ≤ 10 mg QD or the equivalent
 - Local steroid therapies (eg, otic, ophthalmic, intra-articular, or inhaled medications) are acceptable
12. Malignant disease other than that being treated in this study, with the following exceptions:
 - Malignancies that were treated curatively and have not recurred within 2 years prior to study treatment

- Completely resected basal cell and squamous cell skin cancers
- Any malignancy considered to be indolent and that has never required therapy
- Completely resected carcinoma in situ of any type

13. Any medical condition that would, in the Investigator's judgment, prevent the patient's participation in the clinical study due to safety concerns, compliance with clinical study procedures, or interpretation of study results

14. Any major surgical procedure (as judged by the Principal Investigator) within 2 weeks of the planned first administration of study drug. **NOTE:** Minimally invasive procedures such as bronchoscopy, tumor biopsy, insertion of a central venous access device, and insertion of a feeding tube are not considered major surgery and are not exclusionary

15. Pregnant, likely to become pregnant, or lactating women (where pregnancy is defined as the state of a female after conception and until the termination of gestation)

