6.13 Concomitant Therapy

6.13.1 Permitted Concomitant Therapy

In general, concomitant medications and therapies deemed necessary for the supportive care and safety of the patient are allowed. Examples include anti-diarrheal medications, anti-emetics, electrolyte supplementation, intravenous fluids, hematologic growth factors, or blood transfusions. However, hematologic growth factors and blood transfusions should only be administered starting with Cycle 2 to avoid confounding interpretation of potential drug-related toxicities during the DLT evaluation period.

Patients are required to notify the investigational site staff about any new medications, herbal remedies, or dietary supplements taken after the start of the study treatment, regardless of treatment duration. All concomitant medications and significant non-drug therapies (including physical therapy, herbal or natural medications and blood transfusions) administered during the study must be listed on the Concomitant Medications Log or the Surgical and Medical Procedures log in the eCRF.

IV hydration required to manage toxicity associated with the study medications (eg, hypotension) should be recorded in the Concomitant Medications Log in the eCRF.

Palliative radiation therapy to non-target lesions is permitted during the study after consultation with the Sponsor Medical Monitor and should be recorded in the eCRF as concomitant therapy.

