7 STUDY SCHEDULE AND ASSESSMENTS

7.1 Pre-Screening and Screening Period Schedule

All patients will be given both a written and verbal description of the study and allowed adequate time to ask questions and decide whether they want to participate. The Investigator (or an appropriate delegate at the Investigator Site) will obtain written consent from each patient prior to commencing any study-related activities or assessments.

Pre-Screening activities may begin once a patient has signed the study IRB/IEC-approved Pre-Screening ICF. During Pre-Screening the patient's HLA-A*02:01, NY-ESO-1, and LAGE-1A status will be determined to establish patient eligibility. Once confirmed HLA-A*02:01-positive **and** NY-ESO-1- and/or LAGE-1A-positive, the patient will be invited to take part in the full study and provided with the main study information sheet.

There is no window for completion of the Pre-Screening activities. Pre-Screening may be performed while the patient is still on another anti-cancer treatment, prior to experiencing disease progression.

Screening must be completed within 21 days of C1D1; baseline radiological evaluations must be performed within 28 days prior to C1D1. Laboratory and radiological assessments performed as part of standard of care prior to signing the ICF may be used if performed within the Screening window. Screening assessments must be repeated if performed outside of the specified Screening window. Patients may re-screen after abnormal labs or symptoms are corrected or treated, but these should first be discussed and agreed with the Sponsor.

The schedule of assessments for Pre-Screening and Screening is shown in [Table 7-1](#).

Table 7-1: Schedule of Pre-Screening and Screening Assessments

Procedure	Pre-Screening	Screening
Days (relative to first dose)		-21 to -1
Informed consent	X	X
HLA-A*02:01 testing	X	
NY-ESO-1 / LAGE-1A testing (archival or new biopsy)	X	
Demography		X
Inclusion/exclusion criteria		X
Medical history and cancer history		X
Prior anti-cancer therapy		X
Prior/concomitant medications		X
Adverse events		X
Safety Assessments		
Complete physical examination		X
Height and weight		
ECOG performance status		X
Vital signs (body temperature, pulse, respiratory rate, blood pressure, and oxygen saturation)		X
12-lead ECG (triplicate)		X
Hematology panel		X
Chemistry panel		X
Coagulation		X
Urinalysis		X
Thyroid function		X
Serum pregnancy test (women of childbearing potential)		X

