13.2.2 Definitions of Measurable and Non-Measurable Disease

Measurable disease represents the presence of at least 1 measurable nodal or non-nodal lesion. If the measurable disease is restricted to a solitary lesion, its neoplastic nature should be confirmed by cytology/histology.

Measurable lesions (both nodal and non-nodal): The minimum size of a measurable, non-nodal target lesion at Baseline should be no less than double the slice thickness or 10 mm, whichever is greater, eg, the minimum non-nodal lesion size for CT/MRI with 5 mm cuts will be 10 mm).

Lytic bone lesions or mixed lesions with identifiable soft tissue components that can be evaluated by CT/MRI can be considered as measurable lesions, if the soft tissue component meets the definition of measurability. Measurable nodal lesions (ie, lymph nodes), lymph nodes ≥ 15 mm in short axis can be considered for selection as target lesions. Lymph nodes measuring ≥ 10 mm and < 15 mm are considered non-measurable. Lymph nodes smaller than 10 mm in short axis at Baseline, regardless of the slice thickness, are normal and not considered indicative of disease.

Cystic lesions thought to represent cystic metastases can be considered as measurable lesions, if they meet the definition of measurability described above. Simple cysts with non-enhancing walls and low CT density are not considered malignant lesions unless proven by biopsy.

Non-measurable lesions: All other lesions are considered non-measurable, including small lesions (eg, longest diameter < 10 mm with CT/MRI or pathological lymph nodes with ≥ 10 to < 15 mm short axis), as well as truly non-measurable lesions eg, blastic bone lesions, ascites, pleural/pericardial effusion and inflammatory breast disease.

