13.2.4 Definitions of Target and Non-Target Lesions

For the evaluation of lesions at Baseline and throughout the study, the lesions are classified at Baseline as either target or non-target lesions.

Target Lesions: All measurable lesions (nodal and non-nodal) up to a maximum of 5 lesions in total (and a maximum of 2 lesions per organ), representative of all involved organs, should be identified as target lesions and recorded and measured at Baseline. Target lesions should be

selected based on their size (lesions with the longest diameter) and their suitability for accurate repeated measurements (either by imaging techniques or clinically).

Each target lesion must be uniquely and sequentially numbered on the eCRF (even if it resides in the same organ). A sum of diameters (long axis for non-nodal lesions, short axis for nodal) for all target lesions will be calculated and reported as the baseline sum of diameters. The baseline sum of diameters will be used as reference by which to characterize the objective tumor response. Each target lesion identified at Baseline must be followed at each subsequent evaluation and documented on eCRF.

Non-Target Lesions: All other lesions are considered non-target lesions, ie, lesions not fulfilling the criteria for target lesions at Baseline. Presence or absence or worsening of non-target lesions should be assessed throughout the study; measurements of these lesions are not required.

Multiple non-target lesions involved in the same organ can be assessed as a group and recorded as a single item (ie, multiple liver metastases). Each non-target lesion identified at Baseline must be followed at each subsequent evaluation and documented on eCRF.

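### A tumor mass irradiated shortly before the first dose can be a target lesion, so radiotherapy shrinkage could count as a partial response in the Phase II primary endpoint

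*Protocol*

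**What the plan says.** Protocol Section 5.3, criterion 3, excludes "Radiotherapy within 2 weeks of the planned first administration of study drug". Its note then states that "palliative radiotherapy to a limited field, such as for the treatment of bone pain or a focally painful tumor mass, is not exclusionary". No minimum interval to the first dose is attached to that exception.

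Protocol Section 13.2.2 sets a low bar for eligibility on measurability: "Measurable disease represents the presence of at least 1 measurable nodal or non-nodal lesion". Section 13.2.4 takes as target lesions "All measurable lesions (nodal and non-nodal) up to a maximum of 5 lesions in total", to be "selected based on their size (lesions with the longest diameter) and their suitability for accurate repeated measurements". Neither section mentions earlier irradiation.

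Protocol Section 7.1 adds that "baseline radiological evaluations must be performed within 28 days prior to C1D1", and it accepts standard-of-care scans taken inside the window. No text orders the scan relative to radiotherapy.

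The only text that ties radiotherapy to lesion type is Section 6.13.1, on concomitant therapy: "Palliative radiation therapy to non-target lesions is permitted during the study after consultation with the Sponsor Medical Monitor".

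**The concern.** The Phase II primary measure is the confirmed response rate by local assessment, in cohorts with no control arm. Any lasting shrinkage of the target sum is credited to IMCnyeso. By limiting on-study radiotherapy to non-target lesions, the protocol already accepts that an irradiated lesion should not drive the response assessment. A lesion irradiated before target lesions are chosen has no such protection, and the exception in criterion 3 names a painful tumor mass, which may be large and measurable.

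The decision rules turn on very few responses: at least 1 in 9 to continue, and at least 3 in 24 to support further evaluation. One misattributed response can matter.

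**Working it through.** **Inputs from the documents**
- Stage 1: 9 patients, stop at 0 responses. Stage 2: up to 15 more, with at least 3 responses in 24. Response rates 5% and 20%; type 1 error 10%, type 2 error 20% (Protocol Section 9.9.2, SAP Section 4.1).
- Partial response: a fall of at least 30% in the target sum from baseline (Protocol Table 13-2).
- Confirmation at least 4 weeks later (Protocol Section 9.5.2), with a 3.5-week allowance in SAP Section 9.1.1.

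Not in the documents, and so assumed below: how often patients have recent palliative radiotherapy to a measurable lesion, and how much that lesion shrinks.

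**Step 1: reproduce the plan's design.** With X1 responses in the first 9, and continuation whenever X1 ≥ 1:

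P(pass) = Σ over x ≥ 1 of P(X1 = x) × P(Bin(15, p) ≥ 3 − x)

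At p = 0.05:
- P(X1 = 0) = 0.95^9 = 0.630, so P(X1 ≥ 1) = 0.370
- x = 1: 0.2985 × 0.1710 = 0.0510
- x = 2: 0.0629 × 0.5367 = 0.0337
- x ≥ 3: 0.0084
- Sum = 0.093

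At p = 0.20 the same formula gives 0.805. Both agree with the stated error limits.

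**Step 2: when can radiotherapy alone give a partial response?** Let the irradiated lesion form a share w of the baseline sum and shrink by a fraction s, with the other target lesions unchanged. The sum falls by w × s, so a partial response needs w ≥ 0.30 / s.

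| Shrinkage s | Share w needed |
|---|---|
| 30% | 100% |
| 40% | 75% |
| 50% | 60% |
| 80% | 37.5% |
| 100% | 30% |

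The irradiated lesion must be the sole or a dominant target lesion unless it shrinks almost completely.

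**Step 3: effect of one such response, true response rate 5% in the other patients, cohort continued whenever the rule allows**
- Among the first 9: the stage 1 criterion is already met. At least 2 more are needed from the other 23: 1 − 0.95^23 − 23 × 0.05 × 0.95^22 = 1 − 0.3074 − 0.3720 = 0.321.
- Among the last 15: stage 1 must still yield a response, and at least 2 are needed from the other 23. P(X1 ≥ 2) + P(X1 = 1) × P(Bin(14, 0.05) ≥ 1) = 0.0712 + 0.2985 × 0.5123 = 0.224.

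**Step 4: range over an assumed frequency.** Let f be the share of patients scored as responders through radiotherapy alone, independent of drug response, so p = 1 − 0.95 × (1 − f).

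| Assumed f | p | P(pass) |
|---|---|---|
| 0% | 0.050 | 0.093 |
| 2% | 0.069 | 0.186 |
| 5% | 0.0975 | 0.350 |
| 10% | 0.145 | 0.606 |

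Nothing in the documents indicates where f lies.

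**Step 5: does a later rule remove it?**
- Confirmation does not remove shrinkage that lasts.
- Response is read locally; central review is optional (Protocol Section 7.4.3).
- The per-protocol set drops key eligibility violations (SAP Section 4.3.5), and this radiotherapy is permitted.
- SAP Section 9 plans no sensitivity analysis of response.
- Exclusion criterion 13 is a discretionary criterion about a patient's medical condition. It does not govern lesion selection.

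**The case against.** **Section 6.13.1 may already cover part of this.** Its limit applies during the study, and Section 3.4 counts Screening as a study period. A reader might infer that a site may scan early in the 28-day window, list a mass as a target, irradiate it and then dose. That is contestable: on this reading of Section 6.13.1 it is not allowed, and Section 13.2.3 wants the baseline evaluation as near to treatment start as possible. Radiotherapy given before target lesions are chosen remains uncovered on either reading.

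**The rule may exist where we cannot read it.** Section 13.2 is based on RECIST v1.1, which is not part of the documents, and parts of Section 7.4.6 are redacted. The Amendment 2 summary mentions a limit on biopsied lesions as targets that the readable current text does not show, so a lesion rule could sit in redacted text. The point is therefore limited to the readable rules. Section 13.2 does set out its own handling of cystic, bone, split and coalesced lesions, so silence on irradiated ones leaves sites without an instruction.

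**The event may be rare.** With scans every 8 weeks, a response first seen at week 8 would on schedule be confirmed near week 16. Without any drug effect, all other disease would have to stay free of progression and new lesions until then. This stands, and it bears on frequency.

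**It could be spotted.** Prior radiotherapy is collected, individual lesion measurements are listed, and waterfall and spider plots are planned. In a cohort of 24 a careful reader could find such a case. But no rule says what then happens to that response in the primary analysis.

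**Conclusion.** The gap is real in the readable text. Limited-field palliative radiotherapy to a tumor mass is allowed with no minimum interval before the first dose, and the target-lesion rules do not exclude a lesion irradiated before baseline. Its shrinkage could count as a confirmed partial response when that lesion dominates the target sum. The pass probabilities of 0.321 and 0.224, against 0.093, assume that one such response has occurred, a true response rate of 5% otherwise, and continuation whenever stage 1 allows it.

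Three stronger readings are not supported:
- That the design's false-positive rate is 32%. No radiotherapy frequency is given, so the figure is conditional.
- That one such response makes stage 2 automatic. Protocol Section 9.9.2 leaves continuation to the sponsor's discretion.
- That an irradiated non-target lesion which disappears also inflates the response rate. Under Table 13-4 it can only turn a partial into a complete response. Both count, and Phase II requires measurable disease.

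The point deserves a change because it decides which lesions enter the primary endpoint.

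**What to change.** - In Section 13.2.4, and for measurability in Section 13.2.2, state that a lesion irradiated before the first dose may not be a target lesion unless it has progressed on imaging since that radiotherapy.
- Reconcile exclusion criterion 3, Section 6.13.1 and Section 13.2.4, and say whether the limit in Section 6.13.1 covers Screening.
- Where pre-study radiotherapy is given, time the baseline scan that is already required after it when feasible.

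Exclusion criterion 3 stays as written, and no change to the non-target response rules is needed.

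The cost is protocol wording and, at times, a differently timed baseline scan. The downside is that a rare patient whose only measurable lesion was just irradiated would not meet the Phase II measurable-disease criterion.
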